4.3 Supportive Care Guidelines

Compazine or ondansetron in the usual doses may be used to manage constitutional symptoms of nausea and vomiting. Steroids may be added based on the treating physicians discretion. Blood products may be administered at the treating physician's discretion. Growth factors will not be administered during cycle 1, but can be administered in subsequent cycles based on treating physician's judgment.

4.4 Duration of Therapy

In the absence of treatment delays due to adverse events, treatment may

continue until one of the following criteria applies:

- Disease progression,
- Intercurrent illness that prevents further administration of treatment,
- Unacceptable adverse event(s),
- Patient decides to withdraw from the study, or
- General or specific changes in the patient's condition that render the patient unacceptable for further treatment in the judgment of the investigator.

5. DOSING DELAYS/DOSE MODIFICATIONS

On the day of starting each cycle, neutrophil and platelet hematologic parameters must have returned to eligibility values. Furthermore, grade 3 non-hematologic toxicity that is felt to be drug related must return to a grade 2 or better. If these criteria are not met, therapy will be held by 1 week increments for a maximum of 2 weeks. If treatment cannot be given during that time frame the patient will be removed from study.

Any grade 4 hematologic toxicity will result in a dose reduction to the lower dose level for methoxyamine/temozolomide. If this occurs at dose level 1, the dose of temozolomide will be decreased to dose level -1 (75 mg/m²/d for 5 days if in the CNS cohort; 100mg/m² for 5 days if in the non-CNS cohort).

6. AGENT FORMULATION AND PROCUREMENT

6.1 Temozar (Temozolomide)

6.1.1 Availability: Temozar is commercially available.

6.1.2 Chemical Name - The chemical name of temozolomide is 3,4-dihydro-3-methyl-4-oxoimidazo[5,1-d]-as-tetrazine-8-carboxamide.

6.1.3 Molecular Formula - C₆H₆N₆O₂

6.1.4 Mechanism of Action - Temozolomide is not directly active but undergoes rapid non-enzymatic conversion at physiologic pH to the reactive compound MTIC. The cytotoxicity of MTIC is thought to be primarily due to alkylation of DNA. Alkylation (methylation) occurs mainly at the O⁶ and N⁷ positions of guanine.

6.1.5 Pharmacokinetics - Temozolomide is rapidly and completely absorbed after oral administration; peak plasma concentrations occur in 1 hour. Food reduces the rate and extent of temozolomide absorption. Mean peak plasma concentration and AUC decreased by 32 % and 9 %, respectively, and Tmax increased 2- fold (from 1.1 to 2.25 hours) when

temozolomide was administered after a modified high fat breakfast. Temozolomide is rapidly eliminated with a mean elimination half-life of 1.8 hours and exhibits linear kinetics over the therapeutic dosing range. Temozolomide has a mean apparent volume of distribution of 0.4 L/kg (% CV= 13%). It is weakly bound to human plasma proteins; the mean percent bound of drug-related total radioactivity is 15%.

6.1.6 How Supplied - TEMODAR (temozolomide) Capsules are supplied in amber glass bottles with child-resistant polypropylene caps containing the following capsule strengths:

TEMODAR (temozolomide) Capsules **5 mg**: opaque white bodies with green caps. The capsule body is imprinted with two stripes, the dosage strength, and the Schering-Plough logo. The cap is imprinted with “TEMODAR”.

5 and 14 capsule bottles.
5 count - NDC# 0085-3004-02
14 count - NDC# 0085-3004-01

TEMODAR (temozolomide) Capsules **20 mg**: opaque white bodies with yellow caps. The capsule body is imprinted with two stripes, the dosage strength, and the Schering-Plough logo. The cap is imprinted with “TEMODAR”.

5 and 14 capsule bottles.
5 count - NDC# 0085-1519-02
14 count - NDC# 0085-1519-01

TEMODAR (temozolomide) Capsules **100 mg**: opaque white bodies with pink caps. The capsule body is imprinted with two stripes, the dosage strength, and the Schering-Plough logo. The cap is imprinted with “TEMODAR”.

5 and 14 capsule bottles.
5 count - NDC# 0085-1366-02
14 count - NDC# 0085-1366-01

TEMODAR (temozolomide) Capsules **140 mg**: opaque white bodies with blue caps. The capsule body is imprinted with two stripes, the dosage strength, and the Schering-Plough logo. The cap is imprinted with “TEMODAR”.

5 and 14 capsule bottles.
5 count - NDC# 0085-1425-01
14 count - NDC# 0085-1425-02

TEMODAR (temozolomide) Capsules **180 mg**: opaque white bodies with orange caps. The capsule body is imprinted with two stripes, the dosage strength, and the Schering-Plough logo. The cap is imprinted with “TEMODAR”.

5 and 14 capsule bottles.
5 count - NDC# 0085-1430-01

14 count - NDC# 0085-1430-02

TEMODAR (temozolomide) Capsules **250 mg**: opaque white bodies with white caps. The capsule body is imprinted with two stripes, the dosage strength, and the Schering-Plough logo. The cap is imprinted with "TEMODAR".

5 capsule bottles.

5 count - NDC# 0085-1417-01

Store at 25° (77° F); excursions to 15°-30° C (59°-86° F).
[See USP Controlled Room Temperature]

6.1.7 Route of Administration – Oral

6.1.8 Toxicity - The incidence of adverse events in the 158 patients in the Anaplastic Astrocytoma study for whom data are available. In the absence of a control group, it is not clear in many cases whether these events should be attributed to temozolomide or the patients' underlying conditions, but nausea, vomiting, fatigue and hematologic effects appear to be clearly drug-related. The most frequently occurring side effects were nausea, vomiting, headache and fatigue. The adverse events were usually NCI Common Toxicity Criteria (CTC) Grade 1 or 2 (mild to moderate in severity) and were self-limiting, with nausea and vomiting readily controlled with antiemetics. The incidence of severe nausea and vomiting (CTC grade 3 or 4) was 10% and 6%, respectively. Myelosuppression (thrombocytopenia and neutropenia) was the dose-limiting adverse event. It usually occurred within the first few cycles of therapy and was not cumulative.

Myelosuppression occurred late in the treatment cycle and returned to normal, on average, within 14 days of nadir counts. The median nadirs occurred at 26 days for platelets [range 21-40 days] and 28 days for neutrophils [range 1-44 days]. Only 14% (22/158) of patients had a neutrophil nadir and 20% (32/158) of patients had a platelet nadir which may have delayed the start of the next cycle. (See **WARNINGS**). Less than 10% of patients required hospitalization, blood transfusion or discontinuation of therapy due to myelosuppression.

In clinical trial experience with 110-111 women and 169-174 men (depending on measurements), there were higher rates of Grade 4 neutropenia (ANC < 500 cells/ μ L) thrombocytopenia (< 20,000 cells/ μ L) in women than men in the first cycle of therapy: (12% versus 5% and 9% versus 3%, respectively).

In the entire Safety database for which hematologic data exist (N= 932), 7% (4/61) and 9.5% (6/63) of patients over age 70 experienced Grade 4 neutropenia or thrombocytopenia in the first cycle, respectively. For patients less than or equal to age 70, 7% (62/871) and 5.5% (48/879) experienced Grade 4 neutropenia or thrombocytopenia in the first cycle, respectively.

Data released by the European Organization for Research and Treatment of Cancer (EORTC) in January 2014 shows that amongst 44 patients receiving temozolomide

worldwide, hepatic injury, including fatal hepatic failure was identified in patients receiving temozolomide. These events are rare but for patients with liver function abnormalities, the risk/benefit of receiving temozolomide should be considered prior to initiation of this agent.

6.2. METHOXYAMINE HYDROCHLORIDE:

6.2.2.1. Chemistry and Manufacturing Introduction:

Methoxyamine hydrochloride: a small organic amine is soluble in water.

Synonymous: O-methylhydroxyamine hydrochloride

Specifications:

Molecular Formula	CH ₅ NO.HCl
Molecular Weight	83.5
Physical description	White crystal
Melting point	149-153 °C
Moisture	1.0% Max
Purity (GC)	98.2%

There are not any chemical or manufacturing differences between the drug product proposed for clinical use and the drug product used in the animal toxicology trials.

6.2.2.2. Drug Substance:

NSC 3801 is Methoxyamine hydrochloride. Following is a description of the drug substance

Non-Proprietary Names: n.a.

Chemical Names: Methoxyamine hydrochloride,
O-methylhydroxyamine hydrochloride

Other Names: TRC102

CAS Number: 593-56-4

NCI Code: NSC 3801

Chemical Structure: CH₃-O-NH₂•HCl

6.2.2.3. Manufacturer of the Drug Substance:

Manufactured for: Tracon Pharmaceuticals
[name]
[name]

[contact]
[contact]

6.2.2.4. Drug Product:

1. Components and Composition

Methoxyamine HCl Injection (also referred to as TRC102 Injection)

The drug product is a sterile solution of methoxyamine hydrochloride in Water For Injection filled into 10 mL single-use vials. Each vial contains 10 mL of a 15 mg/mL solution for a total of 150 mg of methoxyamine hydrochloride per vial. Vials of Methoxyamine HCl Injection are labeled with the following.

Methoxyamine HCl Injection (TRC102 Injection)
10 mL per vial at 15 mg/mL

Protocol Number	Patient Number	XXX-XX-XXXX Lot No.
------------------------	-----------------------	-------------------------------

For IV/Single use only

Instructions for Use: Give as directed per protocol

Caution: New Drug-Limited by Federal (or United States) law to investigational use

Store at 25°C; excursions permitted to 15-30 °C

TRACON Pharmaceuticals, Inc., [name] USA

2. Methoxyamine HCl Injection Storage and Shipping

Methoxyamine HCl Injection should be stored upright at controlled room temperature (25°C; excursions permitted to 15-30 °C).

3. TRC102 Injection Preparation

Methoxyamine HCl Injection will be prepared in the pharmacy and diluted with normal saline in a 250 mL bag. Following dilution in normal saline, Methoxyamine HCl Injection will be administered at room temperature within 24 hours of preparation if refrigerated or 8 hours of preparation if maintained at room temperature. Depending on the dose and patient weight, multiple vials may be required for a single dose.

The following formulae should be used to calculate the volume of Methoxyamine HCl Injection to be added to normal saline:

- Patient weight (kg) × dose level (mg/kg) divided by Methoxyamine HCl Injection (mg/mL) = volume of Methoxyamine HCl Injection (mL) to be administered.

The volume of Methoxyamine HCl Injection to be administered can be rounded up or down to the nearest 0.1 mL. If an increment of 0.05 mL is calculated, the volume should be rounded up. The calculated volume of Methoxyamine HCl Injection is to be diluted in normal saline. A 250 mL normal saline bag is recommended for this purpose. Appropriate judgment

should be exercised in withdrawing an adequate amount of saline (if any) necessary to permit injection of the appropriate volume of diluted antibody into the appropriate sized normal saline bag.

4. The absorption, distribution, metabolism, and excretions of methoxyamine.

Methoxyamine is a small organic amine; it is very soluble in aqueous solution and plasma. A [¹⁴C]-MX protein-binding study in mouse plasma at 37°C indicated insignificant protein binding. 100% of radiolabelled MX was recovered from the samples after Centrifree processing, indicating a lack of reactivity with plasma proteins.

6.2.3. Toxicology information:

Methoxyamine (MX) is a novel biochemical inhibitor of the base excision repair (BER) pathway. It has potential as a chemotherapeutic agent through its ability to synergize with compounds whose DNA damage is normally repaired by BER, such as the alkylating agent, temozolomide (TMZ). *In vitro* studies and xenograft models have confirmed synergistic cytotoxicity in tumor cells treated with both MX and TMZ.

(a) The toxicity of MX was studied in Fischer 344 rats. MX was administrated as a 5-day continuous IV infusion in sterile water. Twelve dose groups, including vehicle control, 0.25, 0.5, 1.25, 2.5, 5, 10, 15, 20, 50, 200 and 500 mg/kg/day were studied using 4-5 males/dose group. Body weight was measured baseline, and on days 1-5, 8, and 12. Blood was drawn for clinical pathology baseline and on day 8 and 12. Animals were sacrificed on day 12. Histopathology was performed on animals that received vehicle control, 2.5, 20 and 50 mg/kg/day.

Mortality: all rats in the 500 mg/kg/day group were found dead or sacrificed moribund on day 1. All animals in the 200 mg/kg/day group were found dead on day 2.

Clinical Observations, Body Weights: animals given 500 mg/kg/day had bradycardia dyspnea, convulsions, prostration and/or were comatose within the first few hours of the beginning of dosing. There were no statically significant changes in body weight in any group compared to the vehicle control group.

Hematology and Clinical chemistry: these parameters are not available for animals given 200 mg/kg/day. Animals that received 500 mg/kg/day that were sacrificed moribund had elevated AST/ALT (4-6X). A decrease in RBC (25-30%) was noted on day 12 in rats given 50 mg/kg/day.

Histopathology: no drug-related lesions were seen in animals given 20 or 50 mg/kg/day. Conclusions: the maximum tolerated dose of MX given as a 5-day continuous iv infusion in rats is greater than 50 mg/kg/day (> 300 mg/m²/day) but less than 200 mg/kg/day (< 1200 mg/m²/day).

(b) Multiple dose toxicity study of methoxyamine and temozolomide in rats and dogs. The effect of escalating doses of MX on the pharmacology and toxicity of a constant dose of TMZ was assessed in rats and dogs on a 5-day schedule. TMZ was given orally, and MX was administered as a continuous iv infusion.

In rats: vehicle control, MX alone (100 mg/kg/day), TMZ alone (30 mg/kg/day), or 25, 50, 75, or 100 mg/kg/day MX in combination with 30 mg/kg/day TMZ were studied using 10 rats/sex/dose group. Body weights were determined baseline, and on days 1-5, 8, 15, 22, and 33. Blood was drawn for clinical pathology on days 8, 15, 22 and 33. Animals were sacrificed on day 8 or 33, and histopathology was performed.

In dogs: vehicle control, MX alone (15 mg/kg/day), TMZ alone (2.5 mg/kg/day), 5 or 15 mg/kg/day MX in combination with 2.5 mg/kg/day TMZ were studied using 2 males and 2 females/dose group. Due to adverse clinical signs seen in males given 15 mg/kg/day \pm TMZ, females in these dose groups received 10 mg/kg/day MX \pm TMZ. Body weights were determined at baseline, and on days 1-5, 8, 12, 19, 26, and 33. Body temperatures were measured baseline, immediately prior to and at 2 and 4 hours after each TMZ dose, and on day 6-8, 12, 15, 19, 26 and 33. Food consumption was measured daily on days 1-5 and weekly thereafter. Blood was drawn for clinical pathology on days 8, 12, 15, 19, 26 and 33. One animal/sex/group was sacrificed on day 8 or 33, and histopathology was performed.

In summary, in both rats and dogs, MX alone (1200-3000 mg/m²/day in rats and 300 mg/m²/day in dogs) caused dose-limiting neurotoxicity (convulsions, tremors, ataxia, and/or head tilt). TMZ alone caused minimal anemia in dogs (50 mg/m²/day) and minimal to moderate neutropenia in rats (180 mg/m²/day). In rats, TMZ-induced neutropenia increased with increasing doses of MX. Lethality also increased in rats with increasing doses of MX in combination with TMZ. The maximum tolerated dose (MTD) in rats is 25 mg/kg/day MX + 30 mg/kg/day TMZ. In dogs, the combination of MX + TMZ did not produce lethality. The MTD is \sim 10-15 mg/kg/day MX + 2.5 mg/kg/day TMZ. The recommended clinical starting dose of MX is 15 mg/m²/day when given as a 5-day continuous iv infusion in combination with orally administered TMZ. This dose is one-tenth the MTD in the most sensitive species (rat).

Pharmacokinetic interaction studies were performed with TMZ and MX in F344 rats and dogs (M.D. Anderson Cancer Center). TMZ concentrations in rat and dog plasma were analyzed after treatment with TMZ and MX. Results showed that MX did not appear to alter the pharmacokinetics of TMZ in either rats or dogs. (Plasma samples were obtained for TMZ analysis 30 min post-TMZ on day 5 and 10 min before the end of the MX infusion on day 6 for MX analysis.)

(c) *In vitro* studies. *In vitro* bone marrow assays were conducted to determine the effect of MX on the myelotoxicity of TMZ. Granulocyte-macrophage colony-forming units (CFU-GM) were obtained from two human and two murine donors. The study provided evidence that TMZ is likely more potent to murine than human CFU-GM. Single agent

MX was well tolerated in both murine and human CFU-GM. Combination of TMZ with MX shows that MX mildly enhances TMZ toxicity to CFU-GM in both species.

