$$A_{inf} = A(1-e^{-kt}) = 59.50 \text{ mg} (1-e^{-(0.0153/\text{h})(1 \text{ h})}) = 0.90 \text{ mg}$$

$$(k = 0.693/T_{1/2} = 0.693/45.26 \text{ h} = 0.0153/\text{h})$$

Therefore, the total methoxyamine dose (A_{total}) given over 60 minutes by intravenous infusion needed to maintain a C_{max} of 41.4 ng/mL over 60 minutes was estimated as:

$$A_{total} = A + A_{inf} = 59.50 \text{ mg} + 0.90 \text{ mg} = 60.40 \text{ mg}$$

The estimated total dose of methoxyamine given over a 60 minute i.v. infusion needed to produce a Cmax of 41.40 ng/mL (60.40 mg) corresponds to 30 mg/m² (assuming an average BSA of 2 m²). Decreasing this calculated dose by 50% to 15mg/m² provides a rational and safe starting methoxyamine dose to administer intravenously over 60 minutes.

In sum, a single dose of MX administered by 60 minute iv infusion in patients enrolled at dose level 1 (15 mg/m²), represents a conservative initial dose level based on human PK parameters obtained from five patients who received methoxyamine at doses of 15 mg/m²/day IV over five days for a total of fifteen cycles.⁴ This dose was calculated so that expected peak concentration following a single 60 minute IV infusion at dose level 1 will be approximately half the observed maximum concentration observed following 5 day intravenous MX infusion.

Temozolomide is now standard treatment for patients with high-grade gliomas⁵ and is often used in patients with metastatic brain tumors as a radiosensitizer or as a single agent therapy. Temozolomide has excellent brain penetration. However, more than half of all GBM patients have MGMT-induced resistance to this agent.⁶ The FDA noted that there was neurotoxicity as DLT from combining temozolomide with methoxyamine in animal toxicology studies and they advised us to exclude patients with brain metastasis or glioma from the initial Phase I study. We now propose to expand the scope of this study while maintaining the original aims by adding a “dose behind” cohort of patients with brain metastasis or glioma. This cohort will be treated with a 1 hr infusion MX dose that is one dose level below that of patients currently enrolling with advanced malignancies but

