4.1 Agent Administration

For all cycles, TMZ will be given orally for 5 days every 28 days. MX will be given as a single one-hour IV infusion every 28 days. Temozolomide will be administered within 5 minutes following the initiation of methoxamine.

Patients will be treated and monitored in the inpatient setting (Clinical Research Unit) during MX administration (on cycle 1 day 1). A physician will be onsite within the hospital in case an adverse event occurs.

Cohort A (eligible patients with no CNS disease)

DOSE-ESCALATION SCHEDULE		
Dose Level	Dose	
	TMZ (mg/m ² /day) x5days	MX (mg/m ²)
Level -1	100	15
Level 1	150	15
Level 2	150	30
Level 3	150	60
Level 4	150	90
Level 5	150	120
Level 6	150	150

Level 7	200	150
---------	-----	-----

Cohort B (eligible patients with CNS disease)

Dose Level	DOSE-ESCALATION SCHEDULE	
	Dose	
	TMZ (mg/m ² /day) x5days	MX (mg/m ²)
Level -1	75	15
Level 1	100	15
Level 2	150	15
Level 3	150	30
Level 4	150	60
Level 5	150	120
Level 6	150	150
Level 7	200	150

For each cohort, 3 patients will be entered sequentially to each dose level.

- If none of the 3 patients at a dose level experience dose limiting toxicity (DLT) during the first cycle, new patients may be entered at the next higher dose level.
- If 1/3 patients experience a DLT during the first cycle, up to 3 more patients will be treated at the same dose level. If the 1st patient in the expanded cohort (4th at the given DL), experiences no DLT, then the remaining 2 patients can start treatment without a necessary delay.
 - As of protocol v22, if 1/3 patients experience any DLT that is not of a CNS nature in Cohort B dose level 6, we will continue dose escalation to dose level 7 since we have already treated three subjects in Cohort A dose level 6 and seven subjects in Cohort A dose level 7, none of whom experienced non-CNS toxicities
- If 2 or more experience DLT during the first cycle, no further patients are started at that dose and the MTD is the highest dose level in which <2 (of 6) patients develop DLT.
- If the final dose level is deemed the MTD, 6 patients will be treated at this dose level even if a DLT has not been observed.

Select non-hematologic grade 3 or 4 or hematologic grade 4 drug-related toxicities (CTC version 3.0) occurring within the first 28 days of the study will be considered a DLT.

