An LC-MS/MS method for quantitative determination of MX in human plasma was developed. In this method, MX and its stable isotope methoxyl-d₃-amine (MX-d3 as internal standard) were directly derivatized in human plasma with 4-(*N,N*-diethylamino)benzaldehyde. The derivatized MX and IS were extracted by methyl-*tert*-butyl ether, and separated isocratically on a Xterra C18 column (2.1 x 100 mm) using an aqueous mobile phase containing 45% acetonitrile and 0.4% formic acid at a flow rate of 0.200 ml/min. Quantitation of MX was carried out by multiple-reaction-monitoring (MRM) mode of positive turbo-ion-spray tandem mass spectrometry. This method has been validated according to FDA guidelines for bioanalytical method. The linear calibration range for MX was 1.25-500 ng/ml in human plasma with a correlation coefficient ≥ 0.9993 . The intra- and inter-assay precision (%CV) at three concentration levels (3.50, 45.0 and 450 ng/ml) ranged 0.9-1% and 0.8-3%, respectively. The stability studies showed that MX met the acceptable criteria under all tested conditions.

b) Temozolomide determination

Analyses will be performed in the Core Pharmacology laboratory, directed by [name].

2. DNA strand break determination by comet assay.

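### The only methoxyamine preparation formula works in kg and mg/kg, but every patient dose level is in mg/m², so it yields no volume as written

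*Combined protocol and SAP*

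**What the plan says.** The dose tables in the Schema and Section 4.1 set every MX level per square metre. Cohort A runs through 15, 30, 60, 90, 120 and 150 mg/m², and Cohort B uses the same values without 90. Section 2 derives the starting dose on the same basis: a total of 60.40 mg "corresponds to 30 mg/m² (assuming an average BSA of 2 m²"), halved to 15 mg/m². Section 6.2.3 also recommends the clinical starting dose for the 5-day infusion in mg/m² per day.

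Section 6.2.2.4, item 3, directs how the volume for the saline bag is to be calculated and lists one formula: "Patient weight (kg) × dose level (mg/kg) divided by Methoxyamine HCl Injection (mg/mL"). Two other sentences there fit the dose tables no better. One reads "Depending on the dose and patient weight, multiple vials may be required for a single dose". The other mentions "injection of the appropriate volume of diluted antibody into the appropriate sized normal saline bag", although MX is a small organic amine.

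Item 1 of the same section gives the product strength: "Each vial contains 10 mL of a 15 mg/mL solution for a total of 150 mg". The vial label reads "Instructions for Use: Give as directed per protocol".

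MX doses in mg/kg appear only for mice (Section 2) and for rats and dogs (Section 6.2.3).

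**The concern.** The preparation formula and the dose tables use different bases, and the protocol contains nothing to connect them. No mg/kg level, no kg-to-m² conversion and no BSA-based formula is given for patients. The reference to an antibody suggests, without proving, that the text was carried over from another product. The label sends the pharmacist back to the protocol, so there is no independent safeguard on the vial.

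Two things are at stake. The first is safety: the pharmacist must depart from the written rule to prepare a correct dose, and following it with the only MX level available gives a gross overdose. The second is the primary objective. The MTD comes from counting DLTs by dose level, so a patient who did not receive the assigned level contributes a DLT result to the wrong dose.

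**Working it through.** **The plan's own conversion.** Section 2 uses A = 59.50 mg and k = 0.693/45.26 h = 0.0153/h.

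- Infusion part: 59.50 × (1 − e^(−0.0153 × 1)) = 0.90 mg.
- Total: 59.50 + 0.90 = 60.40 mg.
- Per m²: 60.40 / 2 = 30.2, which the plan rounds to 30 mg/m².

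This reproduces, and it confirms that the intended dose in mg is BSA × level.

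**The formula as printed.** Volume = weight (kg) × level (mg/kg) / 15 mg/mL. Weight is recorded and the concentration is known, but the mg/kg level is undefined for every patient level. No volume results.

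**If the mg/m² figure is entered as mg/kg.** The dose becomes weight × level instead of BSA × level, so the error factor is weight/BSA. The documents give no patient weights or heights. Those below are assumptions, with BSA by the Mosteller formula:

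- 45 kg, 150 cm: 45 / 1.369 = 32.9
- 70 kg, 170 cm: 70 / 1.818 = 38.5
- 120 kg, 180 cm: 120 / 2.449 = 49.0

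Worked case at level 1 with an assumed 70 kg and 1.8 m²:

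- Correct: 15 × 1.8 = 27 mg, 27/15 = 1.8 mL, 1 vial.
- Misread: 15 × 70 = 1,050 mg, 1,050/15 = 70 mL, 7 vials.
- Ratio: 1,050/27 = 38.9. Per m² the misread dose is 1,050/1.8 = 583 mg/m², against a highest planned level of 150.

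**Would the volume reveal it?** The recommended bag is 250 mL. The last column is 250 × 15 / level.

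| Level (mg/m²) | Correct volume at 2 m² (mL) | Misread volume at 70 kg (mL) | Heaviest patient whose misread volume is ≤ 250 mL (kg) |
|---|---|---|---|
| 15 | 2.0 | 70 | 250 |
| 30 | 4.0 | 140 | 125 |
| 60 | 8.0 | 280 | 62.5 |
| 90 | 12.0 | 420 | 41.7 |
| 120 | 16.0 | 560 | 31.25 |
| 150 | 20.0 | 700 | 25 |

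Across the assumed weights, a misread volume fits the bag at 15 and 30 mg/m², fits only lighter patients at 60, and fits nobody from 90 upward.

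**Would the PK reveal it?** Appendix C predicts a Cmax of 41.40 ng/mL from 59.961 mg. Assuming linear scaling:

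- 27 mg: 41.40 × 27/59.961 = 18.6 ng/mL.
- 300 mg (150 mg/m² at 2 m²): 207 ng/mL.
- 1,050 mg: 725 ng/mL.

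Section 7 states that "The linear calibration range for MX was 1.25-500 ng/ml in human plasma", so 725 lies above the assay limit.

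**A volume threshold for records.** The largest correct volume at 2.5 m² is 2.5 × 150/15 = 25 mL. The smallest misread volume, at 45 kg and level 1, is 45 × 15/15 = 45 mL. A cut at 25 mL separates the two.

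**The case against.** The assigned dose is never in doubt. Both sets of tables say mg/m², Section 2 shows the BSA conversion, and the study calendar collects height and weight, from which BSA follows. A competent pharmacist would use BSA. The formula is also dimensionally sound: if BSA × level is first expressed per kg, weight cancels and the right volume comes out. The large overdose needs a second mistake, putting a number labelled mg/m² into a slot labelled mg/kg. At the upper levels that mistake would be unmistakable: at 150 mg/m² even a 45 kg patient would need 450 mL.

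Most of this stands as a reason to think gross misdosing unlikely. It does not rescue the instruction. The conversion step that makes the formula work is absent from the protocol, and at 15 and 30 mg/m² the bag size offers no protection.

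Three narrower points also have weight.

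- Section 4.1 reports three subjects at Cohort A level 6 and "seven subjects in Cohort A dose level 7, none of whom experienced non-CNS toxicities". These ten subjects argue against systematic misuse, but only mildly, because the dose-limiting toxicity of MX in animals was neurologic. The volume argument is stronger.
- The 725 ng/mL figure extrapolates linearly about 17-fold (1,050/59.961 = 17.5) beyond a simulation built on five patients. It is an indication only.
- A quieter slip is possible: a fixed kg/m² conversion. With 38.9 kg/m² as the fixed value, the error is 32.9/38.9 − 1 = −15% to 49.0/38.9 − 1 = +26%. The 25 mL threshold would miss nearly all such records. At level 1 and 120 kg the volume would be 120/38.9 = 3.1 mL against a correct 2.4 mL.

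**Conclusion.** The concern holds. The protocol's only MX preparation rule cannot be evaluated with any dose level the protocol defines. This is a units inconsistency in an operative dosing instruction, and it follows from the text alone without any assumption.

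The size of the possible error is conditional. If the mg/m² figure were used as mg/kg, the overdose would be about 33- to 49-fold over the assumed adult range. It could go unnoticed at preparation mainly at 15 and 30 mg/m², and at 60 mg/m² in patients of 62.5 kg or less. The documents do not show that any patient was misdosed. The formula should be corrected because it governs an investigational drug in a dose-finding trial, where the MTD is only as sound as the link between assigned and delivered dose.

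**What to change.** Replace the formula in Section 6.2.2.4, item 3, with:

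volume (mL) = BSA (m²) × dose level (mg/m²) / 15 mg/mL

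State which BSA formula applies and which recorded weight feeds it. As useful additions, print check values at 2 m² (2.0, 4.0, 8.0, 12.0, 16.0 and 20.0 mL for 15, 30, 60, 90, 120 and 150 mg/m²), refer to BSA instead of weight in the sentence on vials, and delete the word antibody.

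Before the dose-DLT analysis, compare each existing preparation record with BSA × assigned level. That comparison catches small conversion errors as well as gross ones. Records above 25 mL (more than 2.5 vials, so 3 opened) deserve immediate attention. Cycle 1 MX Cmax, from samples already planned in Section 7, serves as a cross-check.

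The cost is a short amendment, a pharmacy memo and a review of existing logs. No extra patients or procedures are needed, and height and weight are already collected under the study calendar in Section 8.
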